Two-thirds of women have overweight or obesity, and women of reproductive age have experienced the greatest increase in obesity rates of any group.(1) Obesity during reproductive years is a risk factor for pregnancy complications and higher risk of mortality later in life.(2) Women with cardiovascular (CV) risk factors, such as hypertension (HTN) or diabetes (DM) are at higher risk of obesity-related CV complications, as are women with pregnancy complications such as gestational hypertension, preeclampsia, and diabetes. The Diabetes Prevention Program (DPP) is an intensive in-person program resulting in sustained weight loss.(3,4) Behavioral weight loss (BWL) programs modeled after DPP and adapted to online platforms have shown success in different settings. An online behavioral weight loss program modelled after the DPP may be attractive to postpartum women, who may have difficulty attending in-person sessions due to competing demands of caring for a newborn.(5) The objective of this study is to use a randomized clinical trial to test the feasibility and effectiveness of a 16-week online behavioral weight loss program compared to usual care to promote weight loss in the postpartum period among women with CV risk factors. We will also be testing different behavioral strategies to recruit postpartum women to the study. We will be partnering with collaborators at the University of Connecticut (UConn) who have extensively evaluated this platform in different populations.

2. Overall objectives

The objective of this study is to evaluate the feasibility of an online behavioral weight loss program on weight loss among postpartum women at increased cardiovascular risk. A secondary objective is to evaluate the effectiveness of different behavioral strategies to recruit a diverse population of women to enroll in the study.

3. Aims

3.1 Aim 1: To understand feasibility and compare weight loss between postpartum women participating in an online behavioral weight loss intervention compared to usual care.

3.2 Aim 2: To compare recruitment and enrollment strategies in enrolling postpartum women in a weight loss intervention.

4. Background

Pregnancy represents a life transition when many women become at risk for unhealthy lifestyle habits, such as excess weight gain and limited physical activity. At one year postpartum, nearly one-half of lower-income women will weigh 10 pounds more than their pre-pregnancy weight, and one-third will develop new overweight or obesity onset. Overweight and obesity are risk factors for cardiovascular risk (CV) factors, such as hypertension and diabetes, as well as maternal complications in future pregnancies.

The Diabetes Prevention Program (DPP) is one of the most successful behavioral programs for weight loss and diabetes prevention, however the program is designed to be in-person which is challenging for many women with young children at home. Efforts to develop an on-line version of the DPP program have been successful in motivating weight loss among individuals from

diverse backgrounds and early research suggests that it may be modestly effective in postpartum women. Therefore, we propose a pilot feasibility study to examine opportunities to improve engagement in an online DPP program among postpartum women and measure preliminary efficacy by comparing it to usual care.

5. Study design

5.1 Design

We will conduct a pilot two-arm randomized, controlled trial comparing the effect of an online BWL program (intervention) to usual care on weight loss after 16 weeks. The enrollment process and intervention will all be conducted remotely. All interested participants will be asked to complete a 7-day run-in period during which time they will complete surveys and submit a daily food log. Participants will be randomized 2:1 into the intervention and control arms, respectively. At the end of the 16-week intervention, participants will be asked to complete end-of-study surveys and complete an end-of-study virtual weigh-in.

Study population

We will recruit women who have recently delivered at the Hospital of the University of Pennsylvania or Pennsylvania Hospital. We will recruit women who are 6 weeks – 12 months postpartum at the time of study recruitment and have ≥ 1 CV risk factor.

Trial arms

Arm 1. Usual care: Participants will receive educational resources on weight loss and a digital scale.

Arm 2. Online behavioral weight loss: Participants will receive educational resources on weight loss and a digital scale. Participants will participate in a “Weight Loss 101” virtual session, where they are introduced to successful components of weight loss. They will be enrolled in a 16-week online program that is based on the Diabetes Prevention Program (DPP) and involves weekly brief videos, a self-monitoring platform, and automated feedback.(3,6–8)

Intervention

Participants in all arms will attend a virtual Information session, undergo a 1-week behavioral run-in period, and attend a virtual Kick-off session. (see Study Schema). After completing these steps, all participants will be asked to complete a virtual weigh-in at the start and end of the 16-week intervention. In addition, the intervention arm will receive:

- a. Weight loss and physical activity goals as part of the Weight Loss 101 session. All participants will be asked to lose 10% of their body weight, corresponding to 1-2 lb/week over the 16-week study. Participants will be enrolled in the online behavioral weight loss program. The program involves the following components and described in more detail in Appendix 1:
- b. Weekly multimedia videos (lesson plan): These illustrated videos are < 5 minutes in length and include topics such as stimulus control, goal setting, and problem solving.

Each video is accompanied by online lesson plan that includes additional information and is posted every Monday morning.

- c. Self-monitoring platform (daily log): Participants are asked to track their daily weight, total calories, and exercise minutes and enter it on the website. These can be entered daily or at the end of the week. As long as values are entered before 11:59pm on Sunday night, the participant will receive automated feedback.
- d. Automated feedback: Based upon the metrics entered into the daily log, participants will receive automated feedback by email on Monday morning with specific goal to work on each week. This may focus on reinforcing daily weights, encouraging adherence calorie or exercise goals, or resetting goals. The overall messaging of the automated feedback is supportive.
- e. Access to health coach: Participants will be able to contact study staff if they are encountering barriers to following the lesson plan or meeting their weight loss goals.

5.2 Study duration

This is a 16-week intervention that starts after the 1-week behavioral run-in and attending the Weight Loss 101 session. Overall duration of study from enrollment to final evaluation is 20 weeks.

[figure not shown]
5.3 Target population

Postpartum women with overweight or obesity, age ≥ 18 years with ≥ 1 CV risk factor, including chronic hypertension or diabetes mellitus, or a pregnancy complication placing them at increased CV risk, such as hypertensive disorder of pregnancy or gestational diabetes.

5.4 Accrual

The study population will be drawn from adult postpartum women at Penn (the Hospital of the University of Pennsylvania (HUP) or Pennsylvania Hospital (PAH)). We will aim to randomize 60 participants, 2:1 in the intervention and usual care groups (40 in the intervention and 20 in usual care). As some participants will be excluded during the run-in period (e.g. because they did not complete the daily food log or $BMI < 27$), we will plan to consent 85 patients to reach our goal randomization. Approximately 8,400 deliveries occur annually at Penn. Assuming about 30% will have any hypertensive disorder or diabetes, 60% will have a $BMI \geq 27$ kg/m^2 , and up to 20% may be excluded for other reasons, we estimate that approximately 1,200 women will be potentially eligible (see Figure 1)

Fig 1: Estimated sample size

5.5 Key inclusion criteria

- 1) Age ≥ 18 years;
- 2) Delivered a baby at HUP or PAH within 8 weeks-12 months prior to study enrollment;
- 3) $BMI \geq 27$ kg/m^2

- 4) Diagnosis of one of the following medical conditions: chronic hypertension, gestational hypertension, preeclampsia, eclampsia, gestational diabetes, or diabetes mellitus (type 1 or 2) based on diagnosis codes in the EMR
- 5) Has online access through smartphone or computer and has email address
- 6) Ability to read and provide informed consent to participate in the study

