5.6 Key exclusion criteria

- 1) Delivered prior to 32 weeks gestation in the EMR
- 2) Documentation of fetal demise or neonatal demise in the EMR
- 3) Currently pregnant or planning to get pregnant within the next 5 months
- 4) Does not speak English
- 5) Answers yes to any of the following questions:
 - Are you currently participating in any other weight loss or physical activity studies?
 - Do you have any medical conditions or other reasons why you could not participate in a 16-week weight loss or physical activity program?
- 6) Participants will be excluded after completing the run-in period if they do not complete the daily food log or their baseline BMI is $< 27 \text{ kg/m}^2$

6. Subject recruitment

We will use EPIC to identify a cross-sectional cohort of potentially eligible patients. Given the lag time between identifying potentially eligible patients and enrollment, we will identify women with a delivery occurring between the time of the data pull and 365 days prior. We will identify women based on the inclusion and exclusion criteria above. In order to optimally recruit women with a $\text{BMI} \geq 27 \text{ kg/m}^2$ at time of enrollment, we will use the following BMI criteria as documented in EMR:

- a. Pregravid $\text{BMI} \geq 30$, regardless of delivery BMI
- b. Pregravid $\text{BMI} 28-29.9$ and delivery $\text{BMI} \geq 33$
- c. If pregravid BMI missing, will include delivery $\text{BMI} \geq 33$

Potentially eligible patients will have their current address, phone number, email address, demographics, and clinical history abstracted. We will compare two approaches to patient recruitment (see study schema above, enrollment strategies)

- a. Email: For patients meeting inclusion criteria with a documented email address, we will randomize them to one of two recruitment emails that test behavioral approaches to engaging patients. Group 1 (reserved a spot) will receive an email notifying them that we reserved a spot for them in the upcoming online information session for a weight loss program designed for postpartum women. Group 2 (commit today) will receive an email asking participants if they are ready to commit to their health. Participants will be able to click on an embedded link in the email which will take them to a secure Redcap survey that will allow them to sign up for the virtual information session. Once participants sign up, they will receive a text reminder prior to the information session with the Zoom link. See

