Appendix 2 for text of recruitment emails. For participants who do not respond, a reminder email will be sent 48 hours after the initial email.

- b. Mailer: We will combine participants who received an email but did not respond and patients who do not have an email address documented in the EMR. We will then randomize them to one of two mailer strategies: study mailer alone versus mailer plus gift. The mailer alone group will receive a flyer and mailer that focuses on achieving a healthy lifestyle postpartum and explaining the weight loss study (see Appendices 3 and 4). The mailer plus gift group will receive a mailed package containing the flyer and mailer plus a baby bib inscribed with study logo. Recruitment materials will be sent in waves until the expected number of participants are enrolled.

Patients will be able to sign up for the virtual information session hosted on Zoom through the study website (Redcap). Information on how to sign-up will be included on the mailer. In addition, patients will be able to call or text the study phone number to talk to a clinical research coordinator (CRC) in the Maternal and Child Health Research Center (MCHRC) to learn more about the study and/or sign up for an information session. We will try to accommodate patients who cannot make any of the scheduled sessions by scheduling additional sessions. In order to sign up, participants will need to provide their name, contact information, and date of birth.

As of 9/25/2021, we have reached target randomization using email recruitment alone. In order to compare the mailer versus mailer plus baby gift as outlined in Aim 2, we will continue recruitment using the mail strategy (see Study Schema, enrollment strategies above). When participants click on the Redcap link to sign up for a virtual information session, they will be informed that study enrollment is full. They will have the option to watch a 10-15 minute recorded video of study staff reviewing evidence based approaches to weight loss, which will be posted on the Recap website.

7. Subject compensation

All eligible participants will receive a scale if they complete the 1-week behavioral run-in period. Participants will receive \$30 after completing the 16-week intervention, virtual weigh-in and exit survey at the end of the study. Compensation will be delivered via Greenphire ClinCard.

8. Study procedures

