To compare sample characteristics between arms we will use t-tests or Wilcoxon rank-sum tests for continuous variables and Pearson chi square tests or Fisher's exact tests for categorical variables. Generalized linear mixed effects models will be used to assess for differences in weight, given repeated observations. We will use fixed effects to adjust for study arm, baseline weight, and calendar month, which may reflect seasonal variations that make weight loss harder or easier. We will conduct a number of sensitivity analyses to evaluate the robustness of our findings. All hypothesis tests will be two-sided using a two-sided alpha of 0.05 as our threshold for statistical significance. We will use Stata and/or SAS to analyze the data. We will use multiple imputation for missing data.

10. Investigators

[name], MPH is the co-Principal Investigator (PI) and is an Assistant Professor of Medicine at the Perelman School of Medicine. She is Director of the Women's Cardiovascular Health Program. She has experience running lifestyle interventions among postpartum women.

[name] is the co-Principal Investigator (PI) and is a Professor of Psychology in Psychiatry at the Perelman School of Medicine. She is Director of the Center for Weight and Eating Disorders. She has extensive experience designing and running behavioral weight loss clinical trials.

[name] is a co-investigator. She is Associate Professor in the Department of Allied Health Sciences and Co-Director of the Weight Management Research Group at the University of Connecticut (UConn). She developed the online BWL platform along with collaborators at the University of North Carolina.

The Clinical Research Coordinator has experience with administering studies involving interventions with pregnant and postpartum populations and also has experience training Research Assistants to follow study protocols.

11. Human research protection

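### The postpartum entry window starts at 6 weeks (at recruitment) in Section 5.1 and at 8 weeks (at enrollment) in Section 5.5, nothing reconciles the two, and the weight model omits weeks since delivery

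*Combined protocol and SAP*

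**What the plan says.** The combined protocol and SAP states the postpartum window twice.

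- Section 5.1 (Design, study population): "6 weeks – 12 months postpartum at the time of study recruitment".
- Section 5.5, criterion 2: "Delivered a baby at HUP or PAH within 8 weeks-12 months prior to study enrollment".

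Section 6 then describes the search of the medical record: "we will identify women with a delivery occurring between the time of the data pull and 365 days prior". It gives a reason, "Given the lag time between identifying potentially eligible patients and enrollment", and adds a filter: "We will identify women based on the inclusion and exclusion criteria above". On the email experiment it says: "For patients meeting inclusion criteria with a documented email address, we will randomize them to one of two recruitment emails". On the mail experiment it says: "We will combine participants who received an email but did not respond and patients who do not have an email address documented in the EMR". It also records that target randomization had been reached by 9/25/2021 through email alone, and that later sign-ups are told the study is full.

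Section 9 lists the enrollment rate under each email and mail strategy among the primary outcomes, without defining a numerator or denominator. For the weight outcome it says: "We will use fixed effects to adjust for study arm, baseline weight, and calendar month". Time since delivery is not in that list.

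**The concern.** A woman between 6 and 8 weeks postpartum fits Section 5.1. Whether she fits Section 5.5 depends on how much time separates recruitment from enrollment, and the protocol does not tie either word to a date for this purpose. Two coordinators could apply the rule differently, and a reader of the results could not tell which population was studied.

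Time since delivery also matters for the weight comparison. Participants may enter anywhere from the first weeks postpartum to a year after delivery, and natural weight change plausibly differs over that span. The plan adjusts for calendar month because season may make weight loss harder or easier. The same reasoning applies to weeks since delivery, and with 40 and 20 women a chance imbalance between arms is likely enough to plan for.

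**Working it through.** **1. The plan's own figure.** Section 5.4 gives 8,400 deliveries a year, 30% with a hypertensive disorder or diabetes, 60% with BMI of at least 27, and up to 20% excluded for other reasons:

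8,400 × 0.30 × 0.60 × (1 − 0.20) = 1,209.6

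This reproduces the stated figure of approximately 1,200. It counts a full year of deliveries, so it matches the 0-to-365-day search and neither postpartum window.

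**2. Effect of the lower limit.** Assume deliveries are spread evenly over the year. The share of the pool inside the window on a single date is (365 − 7w)/365 for a lower limit of w weeks.

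| Lower limit | Share of pool | Women |
|---|---|---|
| none | 365/365 = 100% | 1,210 |
| 6 weeks | 323/365 = 88.5% | 1,070 |
| 8 weeks | 309/365 = 84.7% | 1,024 |

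The disputed band is 14 days: 14/365 = 3.8% of the search, or about 46 women. As a share of the 6-week window it is 14/323 = 4.3% (in weeks, 2/46 = 4.3%). Applied to 60 randomized women, 0.043 × 60 is about 2.6.

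**3. Effect on a crude rate, for illustration.** With 60 women randomized, 60/1,070 = 5.6% and 60/1,024 = 5.9%. The choice between 6 and 8 weeks moves the crude rate by about 0.3 percentage points.

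**4. Chance imbalance in time since delivery.** Assume a uniform spread over weeks 6 to 52.

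- SD = 46/√12 = 13.3 weeks.
- SE of the difference in arm means = 13.3 × √(1/40 + 1/20) = 3.6 weeks.
- 95% range of chance differences = ±1.96 × 3.6, or about ±7 weeks.

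Starting at week 8 instead gives SD = 44/√12 = 12.7 and a range of about ±6.8 weeks, so the choice of limit hardly matters here.

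**5. Possible gain from adjustment.** If weeks since delivery correlates r with weight change, adjustment multiplies the residual variance by 1 − r². The documents give no value of r, so a range is assumed.

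| r (assumed) | Residual variance removed | Equivalent sample size, 60/(1 − r²) |
|---|---|---|
| 0.2 | 4% | 62.5 |
| 0.4 | 16% | 71.4 |

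The gain is equivalent to about 2 to 11 more women, before allowing for the one degree of freedom spent.

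**The case against.** The strongest reply is that the two windows refer to different moments. A woman contacted at 6 weeks may well be 8 weeks postpartum when she enrolls, so both statements could be intended. This stands in part: it rules out calling the two statements a certain contradiction. The protocol does not say that this is the intention, though, so the mismatch still needs reconciling.

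A reader might infer several stronger points that the documents do not support.

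- **That the 0-to-365-day search is a third eligibility rule.** It is a screening frame with a stated reason, and the inclusion and exclusion criteria are applied to it.
- **That women outside the window are randomized to emails or mailers.** Section 6 randomizes emails among women who meet the inclusion criteria. It leaves open whether a woman still too early on the search date is contacted at once or held until she qualifies. That is an open question, not a stated practice.
- **That the upper limits conflict.** Both are 12 months. A woman who passes 12 months between contact and enrollment simply fails criterion 2.
- **That early and late exclusions add up as separate losses.** They offset each other. With an 8-week limit, even deliveries and a lag of L weeks (up to 8), the share outside the window at enrollment is (8 − L)/52 + L/52 = 8/52 = 15.4%, whatever L is.
- **That the recruitment comparison is biased.** Both strategies in each comparison draw on the same frame. If a fraction f of contacted women could not enroll, each rate would be multiplied by about 1 − f. Their ratio would be unchanged, and the absolute difference would shrink by the same factor.

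On the covariate, it is fair to say that randomization balances time since delivery in expectation, that ±7 weeks is ordinary chance variation, and that omitting one prognostic variable from a pilot is not an error. All of that stands. The case for including it is precision and protection against chance imbalance at very low cost.

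**Conclusion.** The point holds as an unreconciled entry rule: two lower limits, two reference dates and no linking text. Its size is modest, about 4% of the 6-to-52-week window, or roughly 2 to 3 of 60 women, assuming even deliveries. It affects how the study population is described and, slightly, the absolute enrollment rates. It does not by itself bias the randomized recruitment comparisons.

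The enrollment-rate denominator is undefined rather than contradictory, and the randomized groups in Section 6 supply a natural one.

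Adding weeks since delivery to the weight model is a worthwhile improvement, not the correction of an error. The benefit of 4–16% of residual variance rests wholly on an assumed correlation of 0.2–0.4. Since target randomization has been reached, rewording the window cannot change who entered the trial, but reporting and analysis can still be settled.

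**What to change.** 1. **Entry rule.** Reconcile Sections 5.1 and 5.5 to one postpartum window measured at one named time point. Which limit applies is for the investigators to settle. Report which window, and which date, was actually applied to the women randomized. Cost: a wording change and a sentence in the report.

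2. **Enrollment rate.** State in Section 9 that the denominator for each strategy is every woman randomized to it. Do not restrict it to women inside the window when contacted: someone too early at contact could qualify later and enroll, and would then be in the numerator but not the denominator. Define the numerator as well. Cost: wording only.

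3. **Weight model.** Prespecify weeks since delivery at the baseline weigh-in, calculated from the delivery date in the medical record, as a linear fixed effect alongside arm, baseline weight and calendar month. Do this before the arm comparison is run. Cost: one degree of freedom in about 60 women, with no new data collection. If the correlation with weight change is near zero, that degree of freedom buys nothing.
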